5.3 Adverse Event Reporting Requirements

5.3.1 **Purpose**

Adverse event data collection and reporting, which are required as part of every clinical trial, are done to ensure the safety of patients enrolled in the studies as well as those who will enroll in future studies using similar agents. Adverse events are reported in a routine manner at scheduled times during a trial (please refer to the E2905 Forms Packet for the list of forms with directions for routine adverse event reporting). Additionally, certain adverse events must be reported in an expedited manner for more timely monitoring of patient safety and care. The following sections provide information about expedited reporting.

5.3.2 **Determination of reporting requirements**

Reporting requirements may include the following considerations: 1) whether the patient has received an investigational or commercial agent; 2) the characteristics of the adverse event including the grade (severity), the relationship to the study therapy (attribution), and the prior experience (expectedness) of the adverse event; 3) the phase (1, 2, or 3) of the trial; and 4) whether or not hospitalization or prolongation of hospitalization was associated with the event.

An investigational agent is a protocol drug administered under an Investigational New Drug Application (IND). In some instances, the investigational agent may be available commercially, but is actually being tested for indications not included in the approved package label.

Commercial agents are those agents not provided under an IND but obtained instead from a commercial source. The NCI, rather than a commercial distributor, may on some occasions distribute commercial agents for a trial.

When a study arm includes both investigational and commercial agents, the following rules apply.

- **Concurrent administration:** When an investigational agent(s) is used in combination with a commercial agent(s), the combination is considered to be investigational and expedited reporting of adverse events would follow the guidelines for investigational agents.

Steps to determine if an adverse event is to be reported in an expedited manner:

Step 1: Identify the *type* of event: The descriptions and grading scales found in the revised NCI Common Terminology Criteria for Adverse Events (CTCAE) version 3.0 will be utilized until September 30, 2010 for AE reporting. CTCAE version 4.0 will be utilized beginning October 1, 2010.

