UPDATE: CTEP has released CTCAE Version 5.0 and effective April 1, 2018, all expedited adverse event reporting done through CTEP-AERS will utilize version 5 of the CTCAE. All appropriate treatment areas should have access to a copy of the CTCAE version 5.0. A copy of the CTCAE version 5.0 can be downloaded from the CTEP web site (<http://ctep.cancer.gov>).

Step 2: Grade the event using the NCI CTCAE v 5.0.

Step 3: Determine whether the adverse event is related to the protocol therapy (investigational or commercial). Attribution categories are as follows: Unrelated, Unlikely, Possible, Probable, and Definite.

Step 4: Determine the prior experience of the adverse event.

Expected events are those that have been previously identified as resulting from administration of the agent. An adverse event is considered *unexpected*, for expedited reporting purposes only, when either the type of event or the severity of the event is **NOT** listed in:

- **Arm A** – the current NCI Specific Protocol Exceptions to Expedited Reporting (SPEER)
- **Arm B** – the current NCI Specific Protocol Exceptions to Expedited Reporting (SPEER) for the investigational agent or package insert/protocol for the commercial agent.

NOTE: The NCI SPEER (Specific Protocol Exceptions to Expedited Reporting) is included in Section [5.4](#) of the protocol. FOR THIS PROTOCOL, events listed in the SPEER should be considered EXPECTED if the grade being reported is the same or lower than the grade noted in the parentheses next to the AE in the SPEER. Events listed in the SPEER column should be considered UNEXPECTED if the grade being reported exceeds the grade noted in parentheses next to the AE in the SPEER. The SPEER is presented in the last column of the CAEPR and identified with bold and italicized text.

Step 5: Review the "Additional instructions, requirements, and exceptions for protocol E2905" table in Section [5.3.6](#) for protocol

and/or ECOG-ACRIN specific requirements for expedited reporting of specific adverse events that require special monitoring.

NOTE: For general questions regarding expedited reporting requirements, please contact the NCI AdEERS Help Desk: [contact].

Rev. 6/13

5.3.3

Reporting methods

Rev. Add15

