- Rev. Add14 **NOTE:** A death that occurs > 30 days after the last dose of treatment and is attributed possibly, probably, or definitely to the treatment must be reported within 10 calendar days of learning of the event.

- Expedited AE reporting timelines:
 - **24 Hours; 5 calendar days** – The investigator must initially report the AE via CTEP-AERS within 24 hours of learning of the event followed by a complete CTEP-AERS report within 5 calendar days of the initial 24-hour report.
 - **10 calendar days** – A complete CTEP-AERS report on the AE must be submitted within 10 calendar days of the investigator learning of the event.
 - Any medical event equivalent to CTCAE grade 3, 4, or 5 that precipitates **hospitalization* (or prolongation of existing hospitalization)** must be reported regardless of attribution and designation as expected or unexpected with the exception of any events identified as protocol-specific expedited adverse event reporting exclusions.
 - Any event that results in **persistent or significant disability/incapacity, congenital anomaly, or birth defect** must be reported via CTEP-AERS if the event occurs following treatment with an agent under a CTEP IND
 - Use the NCI protocol number and the protocol-specific patient ID provided during trial registration on all reports.
- * Hospitalizations are defined as lasting 24 hours or longer and these events must be reported via CTEP-AERS.

Additional instructions, requirements and exceptions for protocol E2905

1. Additional Instructions:

- With respect to determining the specific day by which the event must be reported, the day the reporter learns of the adverse event constitutes “Day 0”
- For grade 2 and 3 unexpected events, CTEP-AERS reporting is only required if the event is related to the investigational agent(s); it is not required if the event is related only to the commercial agent(s) included in the protocol treatment.

NOTE: For grade 3 unexpected events with hospitalization lasting ≥ 24 hours (or prolonged hospitalization), an CTEP-AERS report is required even if the event is unrelated to the investigational agent(s).

- For instructions on how to specifically report events that result in persistent or significant disability/incapacity, congenital anomaly, or birth defect events via CTEP-AERS, please contact the AEMD Help Desk at [contact] or [contact].

2. ECOG-ACRIN and Protocol Specific expedited reporting requirements:

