The adverse events listed below also require expedited reporting for this trial:

ECOG-ACRIN specific expedited reporting requirements:

- **Hospitalizations:** Any grade 1 or 2 adverse event which precipitates a hospitalization lasting ≥ 24 hours (or prolongs hospitalization) must be reported via CTEP-AERS within 10 calendar days of learning of the event regardless of the attribution and designation as expected or unexpected.

Protocol specific expedited reporting requirements:

➤ **All grade 3 expected events** with an attribution of definite, probable, or possible, regardless of whether the patient is hospitalized, must be reported via CTEP-AERS within 10 calendar days of learning of the event.

➤ **All ≥ grade 3 thrombo-embolic events**, regardless of the attribution and designation as expected or unexpected and whether the patient is hospitalized, must be reported via CTEP-AERS within 10 calendar days of learning of the event.

➤ **Pregnancies**

Pregnancies and suspected pregnancies (including a positive/inconclusive pregnancy test regardless of age or disease state) occurring while the subject is on Lenalidomide, or within 28 days of the subject's last dose of Lenalidomide, are considered immediately reportable events. **The pregnancy, suspected pregnancy, or positive/inconclusive pregnancy test must be reported via CTEP-AERS within 24 hours of the Investigator's knowledge.** Please refer to [Appendix XIV](#) for detailed instructions on how to report the occurrence of a pregnancy as well as the outcome of all pregnancies.

All occurrences of primary red cell aplasia (PRCA) or a report of anti-erythropoietin antibodies must be reported via CTEP-AERS within 10 calendar days of learning of the event. Report under 'Blood/Bone Marrow - Bone Marrow Cellularity' as grade 4 events.

3. Protocol specific expedited reporting exceptions:

For study arms A and B, the adverse events listed below **do not** require expedited reporting via CTEP-AERS:

➤ Grade 4 expected myelosuppression (unless it results in a hospitalization, in which case, an CTEP-AERS report is required).

5.3.7

Reporting Second Primary Cancers

All cases of second and secondary malignancies [including acute myeloid leukemia (AML) and myelodysplastic syndrome (MDS)], regardless of attribution, that occur following treatment on NCI-sponsored trials must be reported as follows:

1. Submit a completed Second Primary Form within 30 days to ECOG-ACRIN at:

ECOG-ACRIN Operations Office - Boston

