²Pregnancy tests must occur within 10 – 14 days and again within 24 hours prior to initiation of lenalidomide. FCBP with regular or no menstruation must have a pregnancy test weekly for the first 28 days and then every 28 days while on study treatment (including breaks in treatment); at discontinuation of lenalidomide and at day 28 post the last dose of lenalidomide. Females with irregular menstruation must have a pregnancy test weekly for the first 28 days and then every 14 days while on study treatment (including breaks in treatment), at discontinuation of lenalidomide and at Day 14 and Day 28 post the last dose of lenalidomide (see [Appendix X](#): Lenalidomide Risks of Fetal Exposure, Pregnancy Testing Guidelines and Acceptable Birth Control Methods).

³The Lenalidomide Education and Counseling Guidance Document ([Appendix XI](#)) must be completed and signed by a trained counselor at the participating site prior to each dispensing of lenalidomide treatment. A copy of this document must be maintained in the patient records. The Lenalidomide Information Sheet ([Appendix XII](#)) will be given to each patient receiving lenalidomide treatment. The patient must read this document prior to starting lenalidomide study treatment and each time they receive a new supply of study drug.

⁴Only enough lenalidomide for 28 days or one cycle of study treatment (whichever is shorter) may be provided to the patient each cycle.

8. Drug Formulation and Procurement

Rev. 6/13
Rev. 5/17
Rev. Add15

NOTE: As of Addendum #13, all patients who register to the study will use commercial supply of Procrit. Patients who previously received Procrit from the NCI will be switched to the commercially supplied Procrit. Sites will register to the REMS program, via the ESA APPRISE Oncology Program, for commercially supplied epoetin alfa (Procrit). In addition, each site should inform the hospital compliance group responsible for the ESA that the epoetin alfa (Procrit) is being used as part of an approved protocol. Please contact the ESA APPRISE Oncology Program at [name]. Patients/insurance will be charged for the commercial supply of epoetin alfa (Procrit). Only brand Procrit should be ordered through the REMS. Epogen may not be substituted for Procrit.

Vial sizes available:

Single-dose vial: 2000, 3000, 4000, 10,000, and 40,000 Units/1 mL (3).

Multidose vial containing benzyl alcohol: 20,000 Units/2 mL and 20,000 Units/1 mL (3).

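### In Arm B and after crossover, a non-hospitalized grade 3 event due only to epoetin alfa is expedited if it is expected but not if it is unexpected

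*Combined protocol and SAP*

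**What the plan says.** Five places in the protocol bear on this.

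- **Section 5.3.2, general rule.** When an investigational and a commercial agent are given together, "the combination is considered to be investigational and expedited reporting of adverse events would follow the guidelines for investigational agents". Step 3 has the site judge relatedness to protocol therapy of either kind. Step 4 gives Arm B an expectedness reference for the commercial agent as well as for lenalidomide.
- **Section 5.3.6, reporting table.** The heading names lenalidomide as the investigational agent in both arms. For events at least possibly related, the table asks for a report in 10 calendar days for unexpected grade 2, and for unexpected grade 3 with or without hospitalization. Expected grade 3 without hospitalization needs none.
- **Section 5.3.6, Additional Instructions (item 1).** Unexpected grade 2 and 3 events are reported only if related to the investigational agent; "it is not required if the event is related only to the commercial agent(s) included in the protocol treatment". A note directly below keeps the report for unexpected grade 3 events with hospitalization of at least 24 hours, whatever the agent.
- **Section 5.3.6, protocol-specific requirements (item 2).** All expected grade 3 events "with an attribution of definite, probable, or possible, regardless of whether the patient is hospitalized, must be reported via CTEP-AERS within 10 calendar days". No agent is named. Thrombo-embolic events of grade 3 or higher, "regardless of the attribution and designation as expected or unexpected and whether the patient is hospitalized, must be reported via CTEP-AERS".
- **Section 8.** "As of Addendum #13, all patients who register to the study will use commercial supply of Procrit". Epoetin alfa is therefore the commercial agent to which the exemption applies.

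**The concern.** The point of sorting events into expected and unexpected is to give faster attention to what is not yet known about a treatment. A rule that expedites the expected event and releases the unexpected one of the same grade works against that purpose, and the protocol gives no reason for it.

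Epoetin alfa is the component that distinguishes Arm B from Arm A. Attribution to it alone is a realistic case: Section 5.5.7 has epoetin alfa continue while lenalidomide is held for toxicity. In that situation, whether an unexpected non-hospitalized grade 3 event is expedited turns on whether the site also judges it at least possibly related to lenalidomide. Because Section 5.3.5 ties reporting to the institutional review board to events found reportable, subject to local policy, the gap may carry over there.

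Sites also need one answer. Reading 5.3.2 and the table, a site would file the report; reading the Additional Instructions, it would not.

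**Working it through.** No sample size, error rate or event count enters this point, so the check is to apply the rules cell by cell. Take an event in an Arm B or crossover patient, within 30 days of the last dose, at least possibly related to epoetin alfa and not related to lenalidomide.

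| Event related only to epoetin alfa | If unexpected | If expected | Order reversed? |
|---|---|---|---|
| Grade 2, not hospitalized | Table: 10 days; exemption: none | None | No |
| Grade 2, hospitalized 24 h or more | 10 days | 10 days | No |
| **Grade 3, not hospitalized** | **Table: 10 days; exemption: none** | **Table: none; item 2: 10 days** | **Yes** |
| Grade 3, hospitalized 24 h or more | 10 days | 10 days | No |
| Grade 3 or higher thrombo-embolic | Reported | Reported | No |
| Red cell aplasia or anti-erythropoietin antibodies | 10 days | 10 days | No |
| Grade 4 or 5 | 24-hour notice, full report in 5 days | 10 days (grade 4 myelosuppression without hospitalization excepted) | No |

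Three further rules apply across these rows. All deaths on study need an expedited report regardless of cause. Events causing persistent or significant disability, congenital anomaly or birth defect are reported. New malignancies are reported regardless of attribution (Section 5.3.7).

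**How the one cell arises.** The table on its own has the usual order for non-hospitalized grade 3 events: unexpected in 10 days, expected not required. Two later items in the same section each change one entry. Item 1 removes the unexpected report when only the commercial agent is implicated. Item 2 adds the expected report without limiting it by agent. Together they turn the order round.

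**Does item 2 reach events due only to epoetin alfa?** As written, yes. It requires an attribution but names no agent, Step 3 of 5.3.2 counts commercial protocol therapy, and Step 4 supplies a way to call a commercial-agent event expected.

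**Grade 2.** Expected grade 2 events without hospitalization are not expedited either, so nothing is reversed. What remains is that the table and 5.3.2 point to a 10-day report for related unexpected events and item 1 removes it.

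**Placement.** Item 3 of the section is the list of protocol-specific exceptions. It names only grade 4 expected myelosuppression. The commercial-agent exemption is not there but among the Additional Instructions.

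**The case against.** **A signposted exception modifies a table; it does not contradict it.** The text under the table and Step 5 of 5.3.2 both send the reader to the additional instructions. Section 5.3.2 says that the combination follows the investigational-agent guidelines, and those guidelines are 5.3.6, which contains the exemption. It also lists the type of agent among the reporting considerations. This largely stands, and is why the relation to 5.3.2 and the table is called a tension. It does not answer the inversion, because the two rules that produce it sit in the same signposted list.

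**Item 2 may be meant for lenalidomide only.** The section title refers to investigational agents. If so, the inversion disappears, but the text does not say so and 5.3.2 counts the combination as investigational. This is an argument for clarifying the sentence.

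**The exempt events are not lost.** They remain in routine reporting (5.3.1). The toxicity rule in 9.4.1 counts grade 3 or higher regimen-related toxicity in the first 30 patients per arm without reference to expedited reports, and then has 9 more Arm B patients closely monitored. The data monitoring committee reviews safety twice a year (9.7). The exemption also needs attribution to the commercial agent alone. All of this stands and limits the importance of the point.

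A reader might go further and infer that early warning of new epoetin alfa harms has been lost, or that only thrombo-embolic and hospitalized events escape the gap. The rows above show otherwise. Red cell aplasia and antibodies are covered separately, and Section 8.2.13 also classes loss of epoetin effect as a serious adverse event. Nor can the excess deaths described in Section 8.2 be tied to this gap, since every death on study is expedited.

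**Conclusion.** Section 5.3.6 is inconsistent for Arm B and crossover patients in one cell. It covers grade 3 events without hospitalization, related only to epoetin alfa, that are not thrombo-embolic, red cell aplasia or antibody cases, disabling or new malignancies. There the expected event must be reported in 10 calendar days and the unexpected one need not be. At grade 2 the exemption is in tension with 5.3.2 and the table, without an inversion.

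The number of events affected cannot be estimated, because the documents give no rate for this kind of event. A reader might size the problem by counting everyone who receives epoetin alfa: 226/2 = 113 if allocation is 1:1, plus the 60 crossovers in Section 9.3. That would count exposed patients, not affected events. The 60 is an illustration for a confidence-interval width, and it derives from the 212-patient analysis set, not the 226 randomized.

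The conclusion assumes that epoetin alfa is the commercial agent, as Sections 5.3.2, 5.3.6 and 8 indicate, and that item 2 applies to both agents, as worded. It concerns safety reporting only; no endpoint, stopping boundary or efficacy analysis depends on it.

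**What to change.** Amend the sentence in the Additional Instructions of 5.3.6 so that the commercial-agent exemption does not apply to unexpected grade 3 events related to epoetin alfa in Arm B or crossover patients. These would then be reported within 10 calendar days, as the table states and as expected grade 3 events already are.

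In the same amendment, state explicitly whether the exemption is still intended at grade 2. If it is, say in 5.3.2 and under the table that it overrides them for those events, so that the passages agree.

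The cost is one amended sentence with a short clarification, and some additional expedited reports whose number cannot be estimated from the documents. There is no effect on the efficacy analysis.

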5.5 Dose Modifications

NOTE: Although effective April 1, 2018, expedited adverse event reporting done via CTEP-AERS (see Section 5.3) will use CTCAE version 5.0 terminology and grading, routine adverse event reporting and dose modifications outlined below will continue to be based on CTCAE version 4.0 terminology and grading.

Rev. 10/09,
8/10

The toxicity grades below are described using the NCI Common Terminology Criteria for Adverse Events (CTCAE) version 4.0.

All appropriate treatment areas should have access to a copy of the CTCAE version 4.0. A copy of the CTCAE version 4.0 can be downloaded from the CTEP website (<http://ctep.cancer.gov/>).

Rev. 6/11

5.5.1 Subjects will be evaluated for adverse events (AEs) at each visit.

5.5.2 Dose Reductions for Lenalidomide

Table 1 gives the dose levels for the dose reduction steps for adverse events.

Table 1

Dose reductions for Lenalidomide	Pre-treatment ANC \geq 1,000 And PLT \geq 100,000	Pre-treatment ANC \geq 500-999 And PLT \geq 50,000-99,000
Starting dose	10 mg po/day on days 1-21, followed by 7 days of no therapy	5 mg po/day, days 1-21, followed by 7 days of no therapy
Dose level -1	5 mg po/day on days 1-21, followed by 7 days of no therapy	5 mg po every other day for 28 days
Dose level -2	5 mg po every other day for 28 days	2.5 mg po every other day for 28 days

Patients who experience limiting cytopenias after prolonged treatment with 2.5 mg every other day may resume treatment at the same dose upon hematologic recovery.

5.5.3 Dose Modifications for Neutropenia

Hold lenalidomide for a decline in neutrophil count to $< 500/\text{mcL}$ that is not supported by myeloid growth factor administration. Lenalidomide should be resumed at the next dose reduction step when neutrophil count is $> 500/\text{mcL}$. Patients who do not experience neutrophil recovery within 8 weeks should be removed from study treatment and complete all off-study evaluations.

5.5.4 Dose Modifications for Thrombocytopenia

Some MDS patients may develop thrombocytopenia precipitously within the first month of lenalidomide therapy. Therefore, weekly CBCs are assessed during the first eight weeks of the study.

The following are dose interruption/modification guidelines for subjects who develop thrombocytopenia.

5.5.4.1 **For patients with a baseline platelet count
≥ 100,000/mcL;**

5.5.4.1.1 Hold lenalidomide when the platelet count falls to < 30,000/mcL. Lenalidomide should be resumed within eight weeks at the next dose reduction step when the platelet count recovers to ≥ 50,000/mcL. Subsequent cycles should continue at that dose reduction level.

Patients who do not experience platelet recovery within 8 weeks should be removed from study treatment and complete all off-study evaluations.

5.5.4.2 **For patients with a baseline platelet count
<100,000/mcL;**

5.5.4.2.1 Hold lenalidomide for decline in the platelet count ≥ 50% of the baseline value. Lenalidomide treatment should be resumed at the next dose reduction step upon platelet count recovery to ≥ 50,000/mcL. Subsequent cycles should continue at that dose reduction level.

Patients who do not experience platelet recovery within 8 weeks should be removed from study treatment and complete all off-study evaluations.

Baseline plt count	Hold for counts of	Must recover to*
≥ 100,000	< 30,000	≥ 50,000
≥ 60,000 – 99,999	50% of baseline	≥ 50,000
< 60,000	50% of baseline	> 30,000

* Then dose reduce for remainder of cycle. Maintain dose reduction for next cycles, as long as subject meets requirements to start next cycle.

5.5.5 Combined Treatment (Arm B): If, at any time, the Hgb level rises to > 12g/dL, regardless of Hgb rate of rise, the epoetin alfa dose will be withheld until the Hgb level decreases to < 11 g/dL and will be resumed at a decreased dose, as outlined below:

- Epoetin alfa 60,000 U sc QW → 40,000 U sc QW
- Epoetin alfa 40,000 U sc QW → 30,000 U sc QW
- Epoetin alfa 30,000 U sc QW → 20,000 U sc QW
- Epoetin alfa 20,000 U sc QW → 10,000 U sc QW

NOTE: If the Hgb rises due to a transfusion, epoetin alfa will continue to be administered, and the dose level will not change.

If Hgb rate of rise is > 1 g/dL in the 1-week or 2-week period immediately preceding the next epoetin alfa dose or the Hgb level exceeds 11.5 g/dL (and the Hgb is ≤ 12 g/dL), the epoetin alfa dose will be decreased immediately, as described, but will not be withheld. For example, at the week 5 scheduled dosing visit, assess Hgb rate of rise between weeks 4 and 5 and weeks 3 and 5.

NOTE: Dose re-escalation may be allowed in the event of an increased, and then decreased, Hgb. Follow the recommendations for Epoetin alfa adjustment when reinstituted for decline in Hgb.

Rev. 6/11

5.5.6 Lenalidomide Monotherapy (Arm A): For those patients experiencing a rise in hemoglobin ≥ 14 g/dL on Arm A, lenalidomide should be withheld until the hemoglobin is ≤ 12 g/dL, at which time treatment can be resumed according to the dose adjustment recommendations in Table 1 of Section [5.5.2](#). For those patients previously adjusted to the lowest lenalidomide dose, the lenalidomide schedule should be changed to a 2 week treatment schedule every 4 weeks.

